## **11.5. Definition of an adverse event**

### **11.5.1. Adverse event**

An adverse event is any unwanted manifestation that occurred in a patient to whom a medicinal product was administered. It is not necessary for the event to have a causal relation with the treatment or use. Examples of adverse events include, without this list having a limited characteristic:

- Abnormal test results (see in the following for circumstances in which an abnormal test result is an AE);
- Clinically significant symptoms and signs;
- Changes to results of the clinical examination;
- Hypersensitivity;
- Lack of efficacy;
- Drug abuse;
- Medicinal product dependence.

Furthermore, for medicinal products, they can include resultant signs and symptoms of:

- an overdose;
- withdrawal;
- misuse;
- off-label use;
- drug interaction;
- extravasation;
- exposure during pregnancy;
- exposure during lactation;
- a medicinal product error;
- occupational exposure.

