## **8. STUDY QUESTION AND OBJECTIVES**

This observational study, whose primary objective is to evaluate the safety and the rate of discontinuation of treatment because of intolerance, is going to make it possible to describe management of adverse events (dose adjustment, temporary discontinuation, permanent discontinuation of treatment) under real life conditions of use in France.

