### **9.7.2. Analysis of the primary objectives**

The following parameters will be evaluated in order to respond to the primary objectives:

- The percent of patients presenting with adverse events considered related to bosutinib by the participating doctor will be described overall (all grades of seriousness combined, all types of events combined), depending on grade: 1, 2, 3 and 4 and grades 3/4, and by type of event.
- The percent of patients who permanently discontinued treatment with bosutinib following an AE considered related to bosutinib by the participating doctor will be described overall.

Analysis of the primary objectives will be detailed in the statistical analysis plan.

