**Table 5: Requirements for recording of adverse events**

Adverse event	Recorded in the electronic CRF of the study	Reported via NIS AEM Report Form to Pfizer Pharmacovigilance within 24hr following awareness of the event
---------------	---	---

Adverse event	Recorded in the electronic CRF of the study	Reported via NIS AEM Report Form to Pfizer Pharmacovigilance within 24hr following awareness of the event
SAE	All	All
Non-serious AE	All	All
Situations involving exposure to a study medicinal product including exposure in pregnancy, exposure during lactation, medicinal product errors, overdose, misuse, extravasation; lack of efficacy and occupational exposure	All (independently of presence of a concomitant AE) except for occupational exposure	All (independently of presence of an associated AE)  Note: Any associated AE is reported together with the exposure scenario.

For each AE, the participating doctor must look for and obtain sufficient information both to determine the outcome of the adverse event and to evaluate if it satisfies criteria for classification of an SAE (see section entitled “Serious adverse event” in the following).

Adverse events must be reported to Pfizer within 24 hours following awareness of the event by the participating doctor, **whether the event has been considered as related to the study medicinal product or not by the participating doctor.**

In particular, if a serious adverse event is fatal or life-threatening, its reporting to Pfizer must be done immediately, whatever the information available on the adverse event. This time period also applies to all new information (follow-up) relating to reports of previously transmitted adverse events. In rare cases where the participating doctor is not immediately informed of occurrence of an adverse event, the participating doctor must report the event within 24 hours after he/she has become aware of it and report the time when he/she became aware of this adverse event for the first time.

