### **11.5.2. Serious adverse events**

A SAE is any untoward medical occurrence in a patient administered a medicinal or nutritional product (including pediatric formulas) at any dose that:

:

- Causes death;
- Is life threatening;
- Requires hospitalization of the patient or prolongation of hospital stay (see below for circumstances under which it does not constitute an adverse event);
- Results in permanent or important disability or incapacity (important alteration of ability to perform acts of daily living);
- Results in a congenital anomaly or malformation.

Progression of the malignancy during the study (including signs and symptoms of disease progression) should not be reported as a serious adverse event, unless the outcome is fatal during the study or during the period of reporting adverse events. Hospitalization due to signs and symptoms of disease progression should not be reported as a serious adverse event. If the malignant condition has a fatal outcome during the study or during the period for reporting adverse events, then the event leading to death should be reported as an adverse event, and as a grade 5 serious adverse event.

An event will be defined as a medically important event based on medical and scientific judgement. A medically important event may not be immediately life-threatening and/or result in death or hospitalization. However, if it is established that the event can be life-threatening for the patient and/or require an intervention in order to prevent one of the aforementioned outcomes, the medically important event should be reported as serious.

Cases which enter into this category of medically important events are, for example, allergic bronchospasm, requiring intensive care in the emergency room of a hospital or at home, coagulation disorders, seizures which have not resulted in hospitalization, or development of medicinal product dependence or medicinal product abuse.

Furthermore, any suspicion of transmission of an infectious agent, pathogenic or not, by a Pfizer product is considered as a serious adverse event. This event can be suspected by clinical symptoms or test results indicating an infection in a patient exposed to a Pfizer product. The terms “suspicion of transmission” and “transmission” are considered as synonymous.

These cases are considered as unexpected and should be managed as serious cases by the Pfizer Pharmacovigilance Department. These cases can also be reported as a product defect, if applicable.

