#### Lack of efficacy

Cases of lack of efficacy of a Pfizer product must be reported to Pfizer by the participating doctor, independently of the existence of an associated AE/SAE or of the indication of the Pfizer product.

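### Section 11.5.1 makes lack of efficacy an adverse event while 11.2, Table 5 and 11.6 treat it separately, so treatment failure can enter the count of discontinuations for intolerance

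*Protocol*

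**What the plan says.** **Definition.** Section 11.5.1 states that "It is not necessary for the event to have a causal relation with the treatment or use". Its open-ended list, introduced by the words "Examples of adverse events include, without this list having a limited characteristic", has "Lack of efficacy" on it as an event in its own right. Overdose, misuse, exposure and similar situations stand in a second list, where only the signs and symptoms that result from them are AEs.

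**Recording.** Section 11.2 names three types of event: serious AEs, non-serious AEs, and a third group of situations. Table 5 gives that third group its own row, covering "exposure in pregnancy, exposure during lactation, medicinal product errors, overdose, misuse, extravasation; lack of efficacy and occupational exposure". These cases go into the eCRF whether or not an AE accompanies them (occupational exposure excepted). Section 11.6 adds that "Cases of lack of efficacy of a Pfizer product must be reported to Pfizer by the participating doctor", again whether or not there is an associated AE.

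**Endpoints.** Section 9.7.2 defines the first primary parameter as the percentage of patients with an AE the doctor considers related, all types combined, and also by grade and type. The second is "The percent of patients who permanently discontinued treatment with bosutinib following an AE considered related to bosutinib by the participating doctor", described overall only. Section 8 describes the study as one "whose primary objective is to evaluate the safety and the rate of discontinuation of treatment because of intolerance".

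**Carve-out.** The only exclusion of disease-related events is in section 11.5.2: "Progression of the malignancy during the study (including signs and symptoms of disease progression) should not be reported as a serious adverse event". Fatal cases are excepted from it.

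**The concern.** A doctor who follows 11.5.1 enters a bosutinib failure as an AE and must then judge causality. A doctor who follows 11.2, Table 5 and 11.6 enters the same failure as a separate situation with no AE attached. Both comply with the protocol. If the first doctor also judges the event related, the patient counts in the first primary endpoint and, once bosutinib is stopped for good, in the second. The second doctor's patient counts in neither.

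The second endpoint would then mix stops for intolerance with stops for treatment failure, in proportions set by recording and causality habits. Misplaced failures can only add to the numerator, so bosutinib would look less well tolerated than it is. The first endpoint is a general measure of related AEs and is less exposed, because only a patient with no other related AE can be added to it.

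**Working it through.** **1. Does any text keep failure out of the endpoints?**

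| Possible barrier | Where | Does it close the gap? |
|---|---|---|
| AE definition | 11.5.1 | No. Lack of efficacy is listed as an AE |
| Separate category | 11.2, Table 5, 11.6 | Only if the site follows these sections rather than 11.5.1 |
| Causality judgement | 11.4 | Partly. The test is a reasonable possibility that bosutinib caused or contributed to the event; no rule covers a drug that did not work |
| Progression carve-out | 11.5.2 | No. It concerns reporting as a serious AE, and only when the outcome is not fatal |
| Endpoint definition | 9.7.2 | No. All event types combined, no exclusion |
| Reasons for discontinuation | 9.7.3 | No. They are described separately, but patients are not removed from the primary numerator |

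Loss of response has a similar route. Under the abnormal-test rules in 11.5.1, a test result that leads to another treatment is an AE, which can cover a test that prompts a switch.

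**2. The plan's own precision.** Section 9.5 gives a half-width of at most 10% for about 100 patients at a 50% rate (Wald, no continuity correction):

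1.96 × √(0.5 × 0.5 / 100) = 0.098, or 9.8 points. The stated figure reproduces.

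**3. Second endpoint.** Inputs:
- Base 20%: section 7.3 cites about 20% permanent discontinuation after an AE in study 200. It is assumed here to be the rate without any failures.
- f, the share of patients who stop for failure: assumed 5, 10 or 17%. The 17% is the protocol's only figure for stopping for lack of efficacy (section 7.2) and comes from first-line imatinib over 8 years.
- s, the share of those recorded as a related AE: assumed 0 to 100%. The documents give nothing on it.
- The two groups of stops are assumed not to overlap.

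Half-width at the base: 1.96 × √(0.2 × 0.8 / 100) = 0.078, or 7.8 points (95% CI 12.2 to 27.8%).

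Observed percentage = 20 + f × s:

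| f | s = 0 | s = 10% | s = 50% | s = 100% | s at which the shift equals 7.8 points |
|---|---|---|---|---|---|
| 5% | 20.0 | 20.5 | 22.5 | 25.0 | never |
| 10% | 20.0 | 21.0 | 25.0 | 30.0 | 78% |
| 17% | 20.0 | 21.7 | 28.5 | 37.0 | 46% |

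The last column is 7.84 / f.

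**4. First endpoint.** Only patients with no other related AE can be added. If failure is independent of other related AEs and every failure is judged related, the increase is (1 − base) × f. With f = 17%:
- base 50%: 0.50 × 17 = 8.5 points
- base 80%: 0.20 × 17 = 3.4 points
- base 90%: 0.10 × 17 = 1.7 points

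These bases are assumptions too.

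**The case against.** The strongest reply has four parts.

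- **Lack of efficacy is already kept apart.** Section 11.2, Table 5 and section 11.6 all treat it as something that may exist without an AE, against one bullet in 11.5.1. This stands to the extent that the protocol cannot be said simply to record lack of efficacy as an AE. It leaves a contradiction, and either reading is open to a site.
- **Relatedness filters it out.** Only AEs judged related count, and many doctors will attribute failure to the leukaemia. This also stands, and it is why the range starts at zero. But the filter is applied doctor by doctor without guidance on this case, so it does not give a uniform count.
- **The reader can see the split elsewhere.** The first endpoint is reported by type of event, and 9.7.3 describes reasons for discontinuation. That helps for the first endpoint. The second is reported only overall, so its headline figure stays mixed.
- **The SAP will settle it.** Section 9.7.2 does defer analysis detail to the SAP, and a list of coded terms is ordinary SAP content. However, the conflict lies in the protocol text that sites use when recording. Section 9.7 also requires an amendment for a major change to the definition of the primary criteria. Whether this exclusion is a major change can be argued; placing it in the protocol avoids the question.

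A reader might also infer more than the text supports. Section 8 ties intolerance to the discontinuation rate only, so the two primary endpoints are not both intolerance measures. The population is resistant or intolerant to a previous TKI, not resistant throughout, and no rate of stopping bosutinib for failure is given, so it cannot be said that failure will be common. The protocol does not say how study 200 classified lack of efficacy and section 9.7 plans no comparison with it, so a loss of comparability with its 20% is not shown.

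**Conclusion.** The point holds as an internal contradiction on what an AE is, joined to a primary endpoint definition that does not resolve it. The second endpoint is the one at risk, because its stated purpose is narrower than its definition.

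On the assumptions shown, the upward shift lies between 0 and 17 points. It exceeds the sampling half-width of 7.8 points only when failures are fairly frequent and a large share is called related: above 46% of them at f = 17%, above 78% at f = 10%, and never at f = 5%. Both drivers are assumed, and the 17% is borrowed from a different drug, line and duration, so this is a range of what could happen and not an estimate. The effect on the first endpoint is smaller the more patients have another related AE.

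The matter deserves correction because it touches a primary endpoint and the remedy is cheap. It does not invalidate the data collection.

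**What to change.** 1. **Reconcile section 11.5.1 with 11.2, Table 5 and 11.6** on whether lack of efficacy is itself an AE or a separate reportable situation. What is recorded in the eCRF and reported to pharmacovigilance under section 11 stays unchanged.
2. **Second endpoint, section 9.7.2.** State that a permanent discontinuation is not counted when the only related AE behind it is lack of efficacy, loss of response or disease progression. Tabulate these patients under the reasons for discontinuation in 9.7.3.
3. **First endpoint, section 9.7.2.** Present the percentage with and without these terms.
4. **Fix a short list of coded terms** for the three concepts before the analysis.

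The cost is a few sentences in the protocol and the term list. No new data are needed. The reported percentages may fall slightly.

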#### Abnormal test results

The criteria enabling to determine if abnormal test data in an objective test should be reported as an adverse event are as follows:

- The test result is associated with symptoms, and/or
- The test result requires additional diagnostic investigations or a medical/surgical intervention, and/or
- The test result leads to a change to dosage or withdrawal of the patient from the study, to administration of a significant additional concomitant treatment or another treatment, and/or
- The test result is considered as an adverse event by the participating doctor or the sponsor.

The simple repetition of an abnormal test, in the absence of the aforementioned conditions, does not constitute an adverse event. Any abnormal test result which proves to result from an error does not need to be reported as an adverse event.

### **11.5.2. Serious adverse events**

A SAE is any untoward medical occurrence in a patient administered a medicinal or nutritional product (including pediatric formulas) at any dose that:

:

- Causes death;
- Is life threatening;
- Requires hospitalization of the patient or prolongation of hospital stay (see below for circumstances under which it does not constitute an adverse event);
- Results in permanent or important disability or incapacity (important alteration of ability to perform acts of daily living);
- Results in a congenital anomaly or malformation.

Progression of the malignancy during the study (including signs and symptoms of disease progression) should not be reported as a serious adverse event, unless the outcome is fatal during the study or during the period of reporting adverse events. Hospitalization due to signs and symptoms of disease progression should not be reported as a serious adverse event. If the malignant condition has a fatal outcome during the study or during the period for reporting adverse events, then the event leading to death should be reported as an adverse event, and as a grade 5 serious adverse event.

An event will be defined as a medically important event based on medical and scientific judgement. A medically important event may not be immediately life-threatening and/or result in death or hospitalization. However, if it is established that the event can be life-threatening for the patient and/or require an intervention in order to prevent one of the aforementioned outcomes, the medically important event should be reported as serious.

Cases which enter into this category of medically important events are, for example, allergic bronchospasm, requiring intensive care in the emergency room of a hospital or at home, coagulation disorders, seizures which have not resulted in hospitalization, or development of medicinal product dependence or medicinal product abuse.

Furthermore, any suspicion of transmission of an infectious agent, pathogenic or not, by a Pfizer product is considered as a serious adverse event. This event can be suspected by clinical symptoms or test results indicating an infection in a patient exposed to a Pfizer product. The terms “suspicion of transmission” and “transmission” are considered as synonymous.

These cases are considered as unexpected and should be managed as serious cases by the Pfizer Pharmacovigilance Department. These cases can also be reported as a product defect, if applicable.

### Hospitalization

Hospitalization is defined as any initial admission (even for a duration less than 24 hours) into a health institution or any prolongation of an admission.

An admission also includes transfer within the hospital to an intensive care unit (for example, from a psychiatric department to a medical department, from a medical department to a coronary care unit, from a neurology department to an intensive care unit for tuberculosis).

A consultation in the ER does not necessarily constitute a hospitalization; however, an event leading to a consultation in the ER should be evaluated as medically important.

Hospitalization in the absence of an adverse event does not constitute an adverse event in itself and does not need to be reported. For example, the following reasons for hospitalization without an AE are to be reported.

- An admission for social reasons (for example, a patient who has no place to sleep)
- An administrative admission (for example, for a yearly examination)
- An optional admission not associated with a triggering AE (for example, for a scheduled cosmetic surgery procedure)
- Hospitalization for observation in absence of an AE
- Admission for treatment of a pre-existing disorder not associated with development of a new AE nor worsening of a pre-existing condition (for example, for an assessment following persistence of laboratory test abnormalities pre-existing treatment)
- An admission planned by the protocol during the clinical study (for example, for a procedure required by the study protocol)

### **11.6. Situation requiring reporting to pharmacovigilance within 24hr.**

Situations involving exposure during pregnancy, exposure during lactation, a medicinal product error, an overdose, misuse, extravasation, lack of efficacy and occupational exposure are described in the following.

#### Exposure during pregnancy (or exposure in utero)

Exposure in pregnancy occurs if:

1. A woman becomes pregnant or it turns out that she is pregnant while she is receiving or is exposed to the study medicinal product (bosutinib) (for example, environmental exposure), or a woman becomes pregnant or turns out to be pregnant after having discontinued and/or having been exposed to the study medicinal product (bosutinib) (maternal exposure);

An example of environmental exposure would be a case involving direct contact with a Pfizer product in a pregnant woman (for example, a registered nurse reports that she is pregnant and has been exposed to chemotherapy products).

2. A man has been exposed, in the setting of treatment or of environmental exposure, to the study medicinal product (bosutinib) before or around the time period of conception and/or has been exposed during the pregnancy of his partner (paternal exposure).

Generally, cases of prospective and retrospective exposure during pregnancy, whatever the source, are to be reported, whether a concomitant adverse event is present or not, according to procedure for reporting serious adverse events.

If a female patient in the study or the partner of a male patient in the study becomes pregnant or it turns out that she is pregnant during treatment of the patient in the study with the study medicinal product (bosutinib), the participating doctor must report this information to Pfizer, whether an adverse event has occurred or not, in addition to the adverse event report form for non-interventional studies as well as the additional form entitled “Exposure during pregnancy”.

Furthermore, information relating to environmental exposure to the study medicinal product (bosutinib) of a pregnant woman (for example, a female patient reports that she is pregnant and that she has been exposed to a cytotoxic product by inhalation or after having accidentally spilled the product) must be reported to Pfizer, whether an adverse event has occurred or not, in addition to the adverse event report form for non-interventional studies as well as the additional form “Exposure during pregnancy”.

The information transmitted must include the expected date of term of pregnancy (see below for information concerning term of pregnancy).

Follow-up should be initiated to obtain general information on the pregnancy.

Furthermore, follow-up should be initiated to obtain information on the outcome of the pregnancy for all cases which are subject to reporting of exposure during pregnancy whose outcome is unknown.

A pregnancy must be followed up to its full term or up to discontinuation of pregnancy (for example, voluntary termination of pregnancy), and Pfizer must be informed of its outcome.

This information will be provided in the capacity of follow-up of the initial report of exposure during pregnancy. In case of birth of a baby, the structural integrity of the neonate cannot be evaluated at time of birth.

In case of a termination of pregnancy, the reason must be specified and, if possible clinically, the structural integrity of the foetus must be evaluated by visual inspection (unless the results of tests performed before the procedure have concluded in a congenital anomaly and that these results have been reported).

If the outcome of pregnancy corresponds to the criteria of an SAE (for example, an ectopic pregnancy, a spontaneous abortion, fetal death in utero, neonatal death, or a congenital anomaly [for a viable baby, an aborted fetus, fetal death in utero or neonatal death]), the procedures for reporting SAE should be followed.

Additional information on the outcome of pregnancy which are reported as SAE are as follows:

- A spontaneous abortion which includes a miscarriage and fetal retention;
- Neonatal deaths which occur during the month following birth must be reported as SAE, whatever the causal relation. Furthermore, the death of an infant above one month of age should be reported as an SAE when the participating doctor evaluates the death of the infant as related or possibly related to exposure to the study product.

Additional information on exposure during pregnancy can be requested. Follow-ups on outcome at birth will be processed on a case-by-case basis (for example, follow-up of a pre-term birth, of young age to identify developmental retardation).

In the case of paternal exposure, the communication form for information intended for the pregnant partner will be given to the patient participating in the study for his partner. It should be documented that this document has been given to the patient participating in the study for transmission to his partner.

